# 5 Population

This multicenter study will be conducted in up to 8 centers worldwide. The study population will consist of approximately 24 male and female *de novo* adult renal transplant patients. The Investigator must ensure that all subjects being considered for the study meet the following eligibility criteria. Subject selection is to be established by checking through all inclusion/exclusion criteria at screening and confirmed prior to randomization. A relevant record (e.g., checklist) of the eligibility criteria must be stored with the source documentation at the study site.

Deviation from any entry criterion excludes a subject from enrollment into the study.

### 5.1 Inclusion Criteria

Subjects eligible for inclusion in this study have to fulfill all of the following criteria:

- 1. Able to understand the study requirements and provide written informed consent before any study assessment is performed.
- 2. Male or female patients  $\geq 18$  to 70 years of age.
- 3. Recipients of a *de novo* renal allograft from a heart-beating deceased, living unrelated or non-HLA identical living related donor.
- 4. Recipients of a kidney with a cold ischemia time (CIT) < 30 hours; hypothermic machine perfusion within the same timeframe is acceptable.
- 5. Subjects who test negative for SARS-CoV-2 test via molecular testing (PCR)

### 5.2 Exclusion Criteria

Subjects meeting any of the following criteria are not eligible for inclusion in this study.

- 1. Transplant recipients sero-negative for Epstein-Barr virus (EBV).
- 2. Multi-organ transplant recipients.
- 3. Subjects who have received a kidney allograft previously e.g., re-transplant.
- 4. Recipient of a kidney from an HLA identical living related donor.
- 5. Recipient of a kidney from a donor after cardiac death.
- 6. Subjects at high immunological risk for rejection as determined by local practice [(e.g., presence of pre-existing DSA, recipient of high Kidney Donor Profile Index ≥ 85 kidney (where assessed)].
- 7. Subjects with donor specific anti-HLA antibody as measured by complement-dependent cytotoxicity assay (CDC), enzyme-linked immunosorbent assay (ELISA), or flow cytometry within 90 days prior to transplant or as performed per the center's local practice.
- 8. Complement-dependent cytotoxicity (CDC) crossmatch positive transplant (isolated positive B cell crossmatches are not an exclusion criterion).
- 9. ABO incompatible recipient
- 10. History of malignancy of any organ system, except for localized excised non-melanomatous skin lesions or carcinoma in situ of the cervix.

- 11. Subjects with clinically significant laboratory abnormality that would preclude participation in the study (e.g., >2.5 x Upper Limit of Normal (ULN) values for (a) liver function chemistries (ALT, AST, ALP), (b) bilirubin, (c) coagulation studies (INR/PT, aPTT).
- 12. Patient with any of the following:
  - hemoglobin (Hgb) < 8 mg/dL
  - WBC count  $< 2.000/\text{mm}^3$
  - platelet count  $\leq 75,000/\text{mm}^3$ .
- 13. Sero-positive for Human Immunodeficiency Virus (HIV) or Hepatitis B Surface Antigen (HBsAg). Subjects who are sero-positive for Hepatitis C virus (HCV) are excluded without proof of sustained viral response (SVR) after anti-HCV treatment.
- 14. Recipient of a kidney from a donor who tests positive for HIV, HBsAg/HBc positive or HCV.
- 15. History of hypersensitivity to any of the study drugs or to drugs of similar chemical classes (e.g., siplizumab, ATG, TAC, MMF, CS).
- 16. Any additional contraindication to the use of TAC or MMF according to the national labeling information of these products (refer to the local product label).
- 17. Evidence of TB infection (after anti-TB treatment, patients with history of latent TB may become eligible according to national guidelines).
- 18. Patient with severe systemic infections, current or within the two weeks prior to randomization.
- 19. Subjects with any other clinically significant medical condition, active infection or laboratory abnormality that would, in the judgment of the investigator, interfere with the subject's ability to participate in the study.
- 20. Subjects who, in the opinion of the investigator, are not capable of giving informed consent for the study or who are unable or unwilling to adhere to the study requirements outlined in the protocol.
- 21. Use of other investigational products or enrollment in another investigational drug study within 30 days of screening or 5 half-lives of the medication, whichever is longer.
- 22. Pregnant or nursing (lactating) women, where pregnancy is defined as the state of a female after conception and until the termination of gestation, confirmed by a positive human chorionic gonadotropin (hCG) laboratory test.
- 23. Women of child-bearing potential, defined as all women physiologically capable of becoming pregnant, unless they are using highly effective methods of contraception during dosing and for 24 weeks after the study medications have been stopped. Highly effective contraception methods include:
  - Female sterilization (have had surgical bilateral oophorectomy with or without hysterectomy), or tubal ligation at least six weeks before taking study treatment. In case of oophorectomy alone, only when the reproductive status of the woman has been confirmed by follow up hormone level assessment.

- Male sterilization (at least 6 months prior to screening). For female subjects on the study, the vasectomized male partner should be the sole partner for that subject.
- Any of the following:
  - a. Use of oral, injected or implanted hormonal methods of contraception or other forms of hormonal contraception that have comparable efficacy (failure rate <1%), for example, hormone vaginal ring or transdermal hormone contraception.
  - b. Placement of long-acting reversible contraceptives an intrauterine device or intrauterine system.

In case of use of oral contraception women should have been stable on the same brand (or generic equivalent) for a minimum of 3 months before taking study treatment.

Additionally, total abstinence, when in line with the preferred and usual lifestyle of the subject may be an acceptable form of contraception. Period abstinence is not an acceptable form of contraception (e.g., calendar, ovulation, symptothermal, post-ovulation methods) and withdrawal).

Women are considered post-menopausal and not of childbearing potential if they have had 12 months of natural (spontaneous) amenorrhea with an appropriate clinical profile (e.g., age appropriate, history of vasomotor symptoms) or have had surgical bilateral oophorectomy (with or without hysterectomy) or tubal ligation at least six weeks prior. In the case of oophorectomy alone, only when the reproductive status of the woman has been confirmed by follow up hormone level assessment if she considered not of childbearing potential.

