# **Key Exclusion Criteria**

Subjects meeting any of the following criteria are not eligible for inclusion in this study:

- Transplant recipients sero-negative for Epstein-Barr virus (EBV).
- Multi-organ transplant recipients.
- Subjects who have received a kidney allograft previously, e.g., re-transplant.
- Recipient of a kidney from an HLA identical living related donor.
- Recipient of a kidney from a donor after cardiac death.
- Subjects at high immunological risk for rejection as determined by local practice [(e.g., presence of pre-existing DSA, recipient of high Kidney Donor Profile Index ≥ 85 kidney (where assessed)].
- Subjects with donor specific anti-HLA antibody as measured by complement-dependent cytotoxicity assay (CDC), enzyme-linked immunosorbent assay (ELISA), or flow cytometry within 90 days prior to transplant or as performed per the center's local practice.
- Complement-dependent cytotoxicity (CDC) crossmatch positive transplant (isolated positive B cell crossmatches are not an exclusion criterion).
- ABO incompatible recipient.
- History of malignancy of any organ system, except for localized excised nonmelanomatous skin lesions or carcinoma in situ of the cervix.
- Subjects with clinically significant laboratory abnormality that would preclude
  participation in the study (e.g., >2.5 x Upper Limit of Normal (ULN) values for (a) liver
  function chemistries (ALT, AST, alkaline phosphatase (ALP)), (b) bilirubin, (c)
  coagulation studies (INR/PT, aPTT).
- Patient with any of the following: hemoglobin (Hbg) < 8 mg/dL, WBC count ≤ 2,000/mm3 or platelet count ≤ 75,000/mm³.

- Sero-positive for Human Immunodeficiency Virus (HIV) or Hepatitis B Surface Antigen (HBsAg). Subjects who are sero-positive for Hepatitis C virus (HCV) are excluded without proof of sustained viral response (SVR) after anti-HCV treatment.
- Recipient of a kidney from a donor who tests positive for HIV, HBsAg/HBc positive or HCV
- History of hypersensitivity to any of the study drugs or to drugs of similar chemical classes (e.g., siplizumab, ATG, TAC, MMF, CS).
- Any additional contraindication to the use of TAC or MMF according to the national labeling information of these products (refer to the local product label).
- Evidence of TB infection (after anti-TB treatment, patients with history of latent TB may become eligible according to national guidelines).
- Patient with severe systemic infections, current or within the two weeks prior to randomization.

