## 8.4.4.1 Hematology

Hemoglobin, hematocrit, red blood cell (RBC), MCV, MCH, Platelet Count, white blood cell (WBC) and differential count (% and abs).

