	immunomodulatory compound in further investigational studies.  Based on the information outlined above, the risks of administering siplizumab in combination with TAC, MMF, and CS are monitorable, manageable and the benefit-risk assessment in the intended patient population remains positive.	safety events and AEs of special interest, regularly and on an ad hoc basis. Furthermore, a priori defined stopping criteria, infection surveillance and pharmacovigilance by ITB-MED as well as ongoing clinical assessments by Investigator and site staff will be employed to protect individual subject safety during the trial.  Overall, the non-clinical and clinical safety results with siplizumab in human, as well as the comprehensive monitoring plan, a priori defined study stopping criteria and ongoing review by an independent DMC support the continued development of this immunomodulatory compound and conduct of further investigational studies. Moreover, in consideration of the ongoing SARS-CoV-2 pandemic, each center will manage their ongoing transplant program and enrollment of patients in this trial based on the Investigator's clinical judgement and individual patient risk assessment in consideration of both local and per protocol risk mitigation plans.  The overall benefit-risk assessment including the aforementioned mitigation strategies and monitorable and manageable risks of administering siplizumab in this patient population is positive and support the conduct of this clinical trial.	
Section 5.1 Inclusion Criteria		New Text: Subjects who test negative for SAR-CoV-2 test via molecular testing (PCR)	Addition of SARS-CoV-2 as an exclusion criterion
Section 5.2 Exclusion Criteria	hemoglobin (Hbg) < 8 mg/dL	hemoglobin (Hgb) < 8 mg/dL	Correction to units of measure
Section 6.2.1. Identification of Investigational Product	Siplizumab is a humanized IgG1[kappa] class monoclonal antibody, supplied as a clear to slightly opalescent, colorless to slightly brownish, preservative-free solution for infusion.	Siplizumab is a humanized IgG1[kappa] class monoclonal antibody, supplied as a clear to slightly opalescent, colorless to slightly brownish, preservative-free, concentrate for solution.	Clarification that siplizumab is supplied as a concentrate for solution

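### The hemoglobin exclusion is printed in mg/dL in both places it appears, so its numeric limit cannot operate as written

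*Protocol*

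**What the plan says.** Protocol Section 5.2, item 12, lists three blood-count exclusions. The first is "hemoglobin (Hgb) < 8 mg/dL". The Synopsis, under Key Exclusion Criteria, has "hemoglobin (Hbg) < 8 mg/dL". The two differ only in the abbreviation. No other place gives the limit in another unit: Section 8.4.4.1 lists the panel as "Hemoglobin, hematocrit, red blood cell (RBC), MCV, MCH, Platelet Count" and so on without units, and the SAP does not restate the criterion.

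The criteria are meant to be applied strictly. Section 5.2 opens with "Subjects meeting any of the following criteria are not eligible for inclusion in this study", and Section 5 states "Deviation from any entry criterion excludes a subject from enrollment into the study". Section 5 also asks for a record of the eligibility check, such as a checklist, with the source documents. Section 8.4.4 allows one repeat before randomization when a laboratory value named in the criteria is outside its protocol range, and excludes the subject if the repeat is still outside. SAP Section 13 summarizes major deviations from entry criteria to the extent that they can be derived from numeric or coded data.

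The Amendment 1 summary in Appendix 2 has a row for this line of Section 5.2. Its stated reason is "Correction to units of measure". The before and after texts in that row both read mg/dL; only the abbreviation differs.

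**The concern.** An exclusion limit is useful only if some candidates could fall below it. One printed in mg/dL lies far below any hemoglobin value a screening laboratory would report, so the line has no effect if taken literally. Three steps depend on it: the eligibility checklist, the repeat-and-exclude rule in Section 8.4.4, and the entry-criterion deviation summary in SAP Section 13.

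The likelier practical problem is inconsistency. Some sites may silently read the line in another unit, while the deviation program may follow the printed text or a programmer's own reading. Site practice and the reported deviation count could then rest on different rules, with nothing in the documents to say which one governs.

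**Working it through.** **Inputs.** The printed limit is 8 mg/dL (Synopsis; Section 5.2, item 12). The conversions are 1 g = 1,000 mg and 1 L = 10 dL. The documents give no hemoglobin data, so I assume 2 to 18 g/dL as a deliberately wide range for living subjects.

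**Step 1: convert the limit.**
- 8 mg/dL ÷ 1,000 = 0.008 g/dL.
- 0.008 g/dL × 10 = 0.08 g/L.

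**Step 2: compare the assumed range with the limit.**
- Lower end: 2 g/dL = 2,000 mg/dL, and 2,000 ÷ 8 = 250 times the limit.
- Upper end: 18 g/dL = 18,000 mg/dL, and 18,000 ÷ 8 = 2,250 times the limit.

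No value in the range is below 8 mg/dL.

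**Step 3: apply the rule to eight illustrative values.** The last column uses the same numeral in g/dL. It shows only how far the result depends on the unit and is not a statement of the intended limit.

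| Hemoglobin (g/dL) | In mg/dL | Multiple of printed limit | Excluded as printed | Excluded if the unit were g/dL |
|---|---|---|---|---|
| 2 | 2,000 | 250 | No | Yes |
| 3 | 3,000 | 375 | No | Yes |
| 5 | 5,000 | 625 | No | Yes |
| 7 | 7,000 | 875 | No | Yes |
| 8 | 8,000 | 1,000 | No | No |
| 10 | 10,000 | 1,250 | No | No |
| 14 | 14,000 | 1,750 | No | No |
| 18 | 18,000 | 2,250 | No | No |

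The printed rule flags 0 of the 8 values; the same numeral in g/dL flags 4 of the 8.

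**Step 4: follow the printed limit through the plan.** Under Section 8.4.4, no low hemoglobin in this range counts as outside the protocol limit, so neither the repeat test nor the exclusion is triggered. Under SAP Section 13, a rule with units handled literally returns zero hemoglobin deviations for any dataset in this range. A rule that compares the numeral 8 with values stored in g/dL could return some, but it would be applying a criterion that the protocol does not print.

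**Step 5: rule out a text-extraction fault.** The same unit appears in the Synopsis, in Section 5.2 and in both texts of the amendment row. Four matching printings make a reading error unlikely. The finding rests on the current text; the amendment row only supports it.

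**The case against.** The strongest reply is that a severely anemic candidate can still be kept out. Exclusion 11 bars laboratory abnormalities important enough to preclude participation, and its listed limits are examples rather than a closed list. Exclusion 19 bars any other "laboratory abnormality that would, in the judgment of the investigator, interfere with the subject's ability to participate in the study". Hemoglobin is on the screening panel, and Section 8.4.4 requires the investigator to document the relevance of out-of-range values. This stands. A reader might infer that severely anemic subjects must be admitted; the documents do not support that. But both exclusions are matters of judgment: neither supplies a fixed limit, and neither can be programmed as a numeric deviation check.

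A second reply is that the slip is obvious and transplant clinicians would query it or read it as a misprint. Most sites probably would. That reduces the practical effect, but it leaves the governing limit unwritten in a protocol that allows no departure from its entry criteria.

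A reader might also infer that an electronic eligibility check has failed. The protocol has the investigator or a designee confirm eligibility in the data-capture system, but nowhere describes an automated hemoglobin check, so that effect is conditional on how the system was built.

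Finally, the SAP is dated June 2024 and reports the interim analysis as done. Enrollment may be complete, although the documents do not say so. If it is, a correction changes nobody's eligibility, and its remaining value lies in deviation review and reporting.

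**Conclusion.** The concern holds for the text as written. The numeric hemoglobin limit is inoperative in both places where it is stated, and the amendment entry that cites a units correction left the unit alone. No value in the assumed range is excluded, and the lowest is 250 times the printed limit. The conclusion needs only that no screened subject has hemoglobin below 0.008 g/dL. That is a matter of general physiology rather than a figure in the documents, but it is not sensitive to the range chosen. Calling the error a factor of 1,000 requires the further assumption that g/dL was meant, which the sponsor must confirm.

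The scope is narrow: a drafting error in one line of item 12. It touches no endpoint, sample size or analysis method. The documents contain no hemoglobin data, so they cannot show that any subject was wrongly enrolled or that any deviation was missed. The firm consequences are the loss of a fixed limit and an entry-criterion deviation rule that, if programmed literally, cannot find a hemoglobin deviation.

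**What to change.** 1. The sponsor's clinical team confirms the intended unit and limit. This review does not propose either.
2. The Synopsis and Section 5.2, item 12, are corrected together, with one abbreviation. Section 13.4.4 requires a written, approved amendment for any protocol change, so a clarification letter alone may not be enough.
3. The eligibility checklist, any check in the data-capture system and the SAP Section 13 deviation programming are verified against the confirmed limit, with the hemoglobin unit stated in the programming specification.
4. Screening hemoglobin of subjects already enrolled is compared with the confirmed limit, and any departure is handled in the deviation listing and summary. If the database is already locked, the comparison can be reported in the clinical study report.

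The cost is small: one unit in two places, plus a check of values already collected for a planned enrollment of up to 24 subjects. The approval step for the amendment is the main burden.

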#### 1.1.4.3 Teratogenicity and Reproductive Toxicology Data

The reproductive/developmental toxicity profile of siplizumab has not been fully characterized. In consideration of the patient population and overall risk benefit profile, women of childbearing potential must utilize highly effective contraception methods to avoid becoming pregnant while receiving siplizumab and for 24 weeks after the last dose.

Women who are nursing may not participate in this trial. The washout period of 24 weeks after the last dose is justified based on predicted PK profiles at 5 mg/kg, where siplizumab is predicted to be fully cleared from plasma and tissues by 12 weeks. The additional 12 weeks is a safety margin to assure complete clearance of siplizumab and recovery of lymphocyte activity.

Concomitant medications may present a separate reproductive risk and are to be used according to local guidelines and label. Please refer to original package leaflets for complete information and guidance and the risks and potential toxicities of each concomitant medication.

In addition, specific guidance on MPA can be located below.

Mycophenolate (MMF; mycophenolate mofetil or MPA; mycophenolic acid) is a confirmed teratogen associated with an increased rate of spontaneous abortion and congenital malformation compared with other immunosuppressants. MPA containing products carry a warning for female patients in the US and EU who may become pregnant and must not be used during pregnancy unless there is no suitable alternative to prevent transplant rejection. Use during pregnancy is associated with increased risks of first trimester pregnancy loss and pregnancy should be ruled out by use of a sensitive serum or urine test before starting mycophenolate; confirmation immediately before starting the medicine is also recommended.

Females of reproductive potential (FRP) must be counseled regarding pregnancy prevention and planning. Mycophenolate should not be used in women of childbearing potential unless they are using highly effective contraception. Some local labels for MPA recommend male contraception (condom). Due to the risks related to the drug's use during pregnancy, a Risk Evaluation and Mitigation Strategy (REMS) program has been established in the US for products containing mycophenolate and details pertaining to this program are provided in Appendix 4.

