# 16.4 Appendix 4: US-Specific CellCept® Pregnancy and Safety Information

- Use of CellCept® during pregnancy is associated with an increased risk of first trimester pregnancy loss and an increased risk of congenital malformations, especially external ear and other facial abnormalities including cleft lip and palate, and anomalies of the distal limbs, heart, esophagus, and kidney.
- Females of reproductive potential must be made aware of the increased risk of first trimester pregnancy loss and congenital malformations with MPA products and must be counseled regarding pregnancy prevention and planning.
- For those females using Cellcept® at any time during pregnancy and those becoming pregnant within 6 weeks of discontinuing therapy, the Investigator or healthcare practitioner should report the pregnancy to the Mycophenolate Pregnancy Registry ([name]). The Investigator or healthcare practitioner should strongly encourage the subject to enroll in the pregnancy registry.
- Risks and benefits of CellCept® should be discussed with the subject. When appropriate, consider alternative immunosuppressants with less potential for embryofetal toxicity. In certain situations, the subject and her healthcare practitioner may decide that the maternal benefits outweigh the risks to the fetus. If this drug is used during pregnancy, or if the subject becomes pregnant while taking this drug, the subject should be apprised of the potential hazard to the fetus.
- To prevent unplanned exposure during pregnancy, females of reproductive potential should have a serum or urine pregnancy test with a sensitivity of at least 25 mIU/mL immediately before starting CellCept®. Another pregnancy test with the same sensitivity should be done 8 to 10 days later. Repeat pregnancy tests should be performed during routine follow-up visits. Results of all pregnancy tests should be discussed with the subject.
- Females of reproductive potential taking CellCept® must receive contraceptive counseling and use acceptable contraception. Patients must use acceptable birth control during entire CellCept® therapy, and for 6 weeks after stopping CellCept®, unless the subject chooses abstinence (she chooses to avoid heterosexual intercourse completely).
- Patients should be aware that CellCept® reduces blood levels of the hormones in the oral contraceptive pill and could theoretically reduce its effectiveness.

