# Acceptable Contraception Methods for Females of Reproductive Potential using MMF\*

Option 1 Methods to Use Alone  OR Option 2 Choose One Hormonal	Intrauterine device (IUD)     Tubal sterilization     Patient's partner had a vasectomy  Hormone Methods choose 1  Barrier Methods choose 1		
Method AND One Barrier Method			
OR	Estrogen and Progesterone  Oral contraceptive pill Transdermal patch Vaginal ring Progesterone-only Injection Implant	AND	
 
Diaphragm with spermicide
 
Cervical cap with spermicide
 
Contraceptive sponge
 
Male condom
 
Female condom
 

Option 3	Barrier Methods		Barrier Methods
Choose One Barrier Method from Each Column (must choose two methods)	choose 1		choose 1
	
 
Diaphragm with spermicide
 
Cervical cap with spermicide
 
Contraceptive sponge
 
	AND	Male condom     Female condom

\*Females of reproductive potential include girls who have entered puberty and all women who have a uterus and have not passed through menopause.

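### Exclusion 23 accepts a hormonal contraceptive on its own, Appendix 4 accepts one on MMF only with a barrier, and Appendix 4's early repeat pregnancy test is not in the visit schedule

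*Protocol*

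**What the plan says.** **Entry rule.** Exclusion 23 (Protocol 5.2) excludes women of childbearing potential "unless they are using highly effective methods of contraception during dosing and for 24 weeks after the study medications have been stopped". The methods it accepts include "Use of oral, injected or implanted hormonal methods of contraception", with no barrier. Two conditions are attached: a failure rate below 1% for other hormonal forms, and three months' stability on one brand or its generic equivalent for oral use.

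**MMF rule.** Appendix 4 obliges females of reproductive potential taking CellCept to use acceptable contraception, and gives three options:
- an IUD, tubal sterilization or partner vasectomy, each sufficient alone;
- a hormonal method paired with a barrier (the row reads "Method AND One Barrier Method");
- two barriers.

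Abstinence is a further exception. The appendix also warns: "Patients should be aware that CellCept® reduces blood levels of the hormones in the oral contraceptive pill and could theoretically reduce its effectiveness".

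**Testing.** Appendix 4 asks for a pregnancy test immediately before CellCept and then: "Another pregnancy test with the same sensitivity should be done 8 to 10 days later". It adds repeats at routine follow-up visits. Section 8.4.4.5 requires a negative test taken no more than 72 hours before transplant and refers to Appendix 1 for the rest.

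**Duration.** Section 1.1.4.3 requires contraception "while receiving siplizumab and for 24 weeks after the last dose". Appendix 4 requires it throughout CellCept therapy and for 6 weeks afterwards.

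**The concern.** Section 5 makes the inclusion and exclusion criteria the check on entry, with a record such as a checklist kept at the site. Visits then follow Appendix 1. A site that works from those two texts alone would accept a woman on a pill, start MMF within 24 hours of reperfusion (6.4.1), and have no scheduled prompt for another pregnancy test until Month 3. A site that works from Appendix 4 would ask her to add a barrier and would retest her in the second week. Both sites would be following the protocol. What is at stake is possible fetal exposure to a drug the protocol itself calls a confirmed teratogen. The trial's statistical conclusions are not at stake.

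**Working it through.** No figure in the plan needs reproducing, because the trial has no power calculation and this point does not depend on one. The check is a comparison of texts, with short day counts for testing and duration.

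**1. Methods**

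| Method | Exclusion 23 | Appendix 4 (on MMF) |
|---|---|---|
| Hormonal alone | accepted | not accepted |
| Hormonal plus barrier | accepted | accepted |
| Two barriers | not listed | accepted |
| IUD alone | accepted | accepted |
| Tubal ligation | accepted | accepted |
| Partner vasectomy | accepted | accepted |
| Total abstinence | may be accepted | accepted |

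Two rows disagree, in opposite directions.

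**2. Does another text close the gap?**
- Section 1.1.4.3 asks for highly effective contraception on mycophenolate, but Exclusion 23 defines that term to include a hormonal method alone.
- Section 1.1.4.3 also refers to local labeling for contraception on MPA. It does not state the barrier condition.
- Exclusion 16 covers label contraindications to TAC or MMF, and Exclusion 20 covers unwillingness to follow study requirements. Neither mentions a barrier.

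**3. Testing**
- The readable Appendix 1 pregnancy row shows screening and Months 3, 6, 9 and 12. Month 3 is Day 84. The table is damaged in the text available, so this reading should be checked against the source.
- Longest gap to the next scheduled test: 3 days (72 hours before transplant) + 84 = 87 days, before visit windows.
- If the pre-MMF test falls on Day 0 or Day 1, Appendix 4's second test falls between Day 0 + 8 = Day 8 and Day 1 + 10 = Day 11. The first scheduled post-transplant test is then 84 − 11 = 73 to 84 − 8 = 76 days later than that.

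**4. Duration**

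Assume for illustration that MMF stops at the last visit, Day 336. In practice it may continue.
- Section 1.1.4.3, counted from the Day 4 siplizumab dose: 4 + 168 = Day 172.
- Appendix 4: 336 + 42 = Day 378.
- Exclusion 23, if its study medications include MMF: 336 + 168 = Day 504.

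Exclusion 23 does not say which drug starts its clock. Section 12.3 counts siplizumab, TAC, MMF and CS when it computes the duration of study medication, which favors the last reading without settling it. The siplizumab clock in 1.1.4.3 has no starting point for the planned rATG subjects (4 + 4 = 8).

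**5. Who is covered**

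Exclusion 23 lists tubal ligation as a contraceptive method for women of childbearing potential. It then treats women with "or tubal ligation at least six weeks prior" as not of childbearing potential. The Appendix 4 footnote includes "all women who have a uterus and have not passed through menopause". Both texts accept tubal ligation as sufficient, so this difference affects only pregnancy testing and counseling.

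**The case against.** The strongest reply is that the texts are layers and not rivals. Exclusion 23 is an entry rule and Appendix 4 is a mandatory rule for women on MMF. A woman enrolled on a pill who adds a barrier satisfies both. Section 1.1.4.3 itself treats concomitant drugs as a separate reproductive risk and directs the reader to Appendix 4. This stands: the protocol does not permit hormonal-only use on MMF. What remains is that the entry check does not ask about the barrier and does not refer to Appendix 4, while two-barrier users are absent from Exclusion 23's list.

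The repeat test is worded as a recommendation and is already in the protocol. That is true, but a site that follows Appendix 1 would not see it.

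Appendix 4 is US-specific, and Section 5 speaks of up to 8 centers worldwide. The synopsis, however, limits the trial to up to 5 US sites, so Appendix 4 applies there. The site statements also disagree with each other.

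Two stronger readings are tempting, and the documents do not support either:
- **That Appendix 4 demands a hormonal method plus a barrier from all women taking MMF.** It does not. An IUD, tubal sterilization, partner vasectomy, two barriers or abstinence also qualify, and the rule covers only females of reproductive potential.
- **That the contraception obligation lapses at Day 172 while MMF continues.** That takes the siplizumab sentence in 1.1.4.3 and applies it to MMF. The same section separately requires highly effective contraception with mycophenolate, and Appendix 4 requires contraception for the whole course of therapy.

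**Conclusion.** The point holds as a contradiction between stated rules. A hormonal method alone passes Exclusion 23 and fails Appendix 4; two barriers pass Appendix 4 and are not listed in Exclusion 23. All subjects receive MMF, so the mismatch matters from the start of treatment. Appendix 4's early repeat test has no place in the readable schedule, and the durations after treatment are stated in three ways without a common starting drug. The tubal-ligation difference is minor.

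The number of women affected cannot be estimated: enrolment is up to 24 subjects aged 18 to 70, and no expected number of women of childbearing potential is given. No endpoint, analysis set or summary in the SAP changes. The conclusion rests on Appendix 4 applying at the US sites and on the Appendix 1 row having been read correctly. Which contraception rule, duration or test schedule is clinically right is not judged here.

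**What to change.** Reconcile Sections 1.1.4.3, 5.2 (Exclusion 23) and 8.4.4.5 with Appendix 1 and Appendix 4, so that they share:
- one list of accepted methods;
- one definition of childbearing or reproductive potential;
- durations that name the drug whose last dose starts each clock, including for the rATG arm;
- one pregnancy-test schedule.

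Carry the result into the eligibility criterion and the Appendix 1 row, since those are what sites apply at entry and at visits. The sponsor's clinical and regulatory leads decide which text governs.

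The cost is amendment wording, a consent-form update and an edit to one schedule row. It may add one urine or serum test that Appendix 4 already asks for. The SAP reports that the interim analysis has been done, so for subjects already well past transplant the duration wording is the part that can still matter.
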